6.5.1.1 Grading of Infusion Reactions

Infusion reactions will be categorized as follows:

- Grade 1: mild reaction; infusion interruption not indicated, intervention not indicated; Note: although interruption in infusion is not indicated, temporary rate reduction indicated before resuming original rate, as patient tolerates (see **Section 6.5.1.3**);
- Grade 2: therapy or infusion interruption indicated but responds promptly to symptomatic treatment [e.g., antihistamines, non-steroidal anti-inflammatory drugs (NSAIDS), narcotics, IV fluids]; prophylactic medications indicated for ≤ 24 hours;
- Grade 3: prolonged (e.g., not rapidly responsive to medication and/or brief interruption of infusion); recurrence of symptoms following initial improvement; hospitalization indicated for clinical sequelae (e.g., renal impairment, pulmonary infiltrates);
- Grade 4: life-threatening consequences; pressor or ventilatory support indicated;
- Grade 5: death.

The above grading scale is the CTCAE v 4.03 grading scale for CRS, which is nearly identical to the CTCAE v 4.03 grading scale for infusion reaction and allergic reaction, and therefore considered appropriate for grading all infusion reactions in this study, irrespective of the underlying mechanism of the reaction. The Sponsor's Medical Monitor or designee should be contacted immediately if questions arise concerning the grade of the reaction.

6.5.1.2 Premedications and Prophylaxis

No specific prophylactic pre-infusion regimen is recommended for pembrolizumab unless a patient has an infusion reaction with pembrolizumab or MGA271 infusion (see below). For MGA271, the following suggested guidelines (which may be modified by the investigator) are measures to be followed to avoid potential infusion reactions.

Prior to first infusion (guidelines to be followed):

- Acetaminophen 650 mg
- Diphenhydramine 50 mg or appropriate dose of equivalent H1 antagonist
- Ranitidine 300 mg or appropriate dose of equivalent H2 antagonist at the discretion of the investigator
- Hydrocortisone 50 to 100 mg suggested or doses up to 10-20 mg dexamethasone may be administered (dose selected at the discretion of the Investigator)

Prior to subsequent MGA271 infusion, investigators may use the following premedications as considered indicated (suggested guidelines):

- Acetaminophen 650 mg
- Diphenhydramine 50 mg or appropriate dose of equivalent H1 antagonist
- Ranitidine 300 mg or appropriate dose of equivalent H2 antagonist
- Optional hydrocortisone not typically needed after first dose. However, for patients who had infusion reactions not adequately or only moderately controlled with acetaminophen, diphenhydramine, or ranitidine, subsequent doses may be tapered at the discretion of the Investigator.

6.5.1.3 Management of Observed Infusion Reactions

The following are treatment guidelines (which may be modified as needed by the Investigator according to the best practices of medicine) for infusion reactions. Note that these apply to MGA271, pembrolizumab, and MGA012:

Grade 1

- Slow the infusion rate by 50%.
- Monitor the patient for worsening of condition.
- Continue rate at 50% reduction and increase dose rate to the original rate by doubling the infusion rate after 30 minutes, as tolerated to the initial rate. Consideration can be given to beginning all subsequent infusions at 50% rate and increasing as tolerated.

- On days when both pembrolizumab and MGA271 or MGA271 and MGA012 are given on the same day and a patient has an infusion reaction with pembrolizumab or MGA012, the MGA271 infusion can be given (without prophylactic medications) on the same day if the infusion reaction resolves within 3 hours. For scheduling purposes, the MGA271 infusion may be given the next day if the reaction lasts greater than 3 hours.
- If a patient has an infusion reaction with pembrolizumab or MGA012, prophylactic preinfusion medications should be given prior to all subsequent pembrolizumab or MGA012 infusions as written below for Grade 1 infusion reactions.
- If a patient has an infusion reaction with MGA271 on either day when it is administered after pembrolizumab, or after MGA012, or given alone, prophylactic preinfusion medications should be given prior to all subsequent MGA271 infusions as written below.
- The following prophylactic preinfusion medications are recommended prior to future infusions of MGA271 and/or pembrolizumab, and/or MGA012 for patients who experience Grade 1 infusion reactions: diphenhydramine 50 mg (or equivalent) and/or acetaminophen 650 mg at least 30 minutes before additional study drug administrations.

Grade 2

- Stop the infusion.
- Administer diphenhydramine hydrochloride 25-50 mg IV, acetaminophen 650 mg orally for fever, and oxygen and bronchodilators for mild bronchospasm.
- Resume the infusion at 50% of the prior rate once the infusion reaction has resolved or decreased to Grade 1. The rate may then be escalated to the original rate after 30 minutes, as tolerated. Consideration can be given to beginning all subsequent infusions at 50% rate and increasing as tolerated.
- Monitor for worsening condition. If symptoms recur, discontinue the infusion; no further study drug will be administered at that visit.
- When both pembrolizumab and MGA271 or MGA012 and MGA271 are given on the same day and a patient has an infusion reaction with pembrolizumab or with MGA012:
 - The MGA271 infusion can be administered on the same day if the infusion reaction resolves within 3 hours. The MGA271 infusion may be given the next day if the infusion reaction last longer than 3 hours.
 - Premedication of diphenhydramine hydrochloride 25-50 mg IV and acetaminophen 650 mg orally should be administered 30 minutes prior to the MGA271 dose. If no corticosteroids were given for the pembrolizumab or

MGA012 infusion reaction, hydrocortisone 50-100 mg IV or equivalent may be considered prior to MGA271 administration.

- Prophylactic pre-infusion medications should be given prior to all subsequent pembrolizumab or MGA012 infusions. Patients who experience Grade 2 infusion reaction should be pre-medicated with diphenhydramine hydrochloride 25-50 mg IV and acetaminophen 650 mg orally for subsequent doses of pembrolizumab.
- If a patient has an infusion reaction with MGA271 on any of the days that it is administered after pembrolizumab or after MGA012, or given alone, prophylactic preinfusion medications should be given prior to all subsequent MGA271 infusions.
- For patients with Grade 2 infusion reactions despite premedication with diphenhydramine and acetaminophen, corticosteroids (hydrocortisone 50-100 mg IV or equivalent) should be considered for acute management of the event and should be added to the premedication regimen for subsequent dosing of pembrolizumab and/or MGA271 or subsequent dosing of MGA012 and/or MGA271.

Grade 3

- STOP THE INFUSION AND DISCONNECT THE INFUSION TUBING FROM THE PATIENT.
- TO AVOID EXACERBATION OF INFUSION REACTION OR CRS: DO NOT FLUSH THE TUBING – ASPIRATE RESIDUAL DRUG FROM THE PORT LUMEN.
- Administer diphenhydramine hydrochloride 25-50 mg IV, hydrocortisone 25-100 mg IV (or equivalent), and other medications/treatment as medically indicated. Higher doses of corticosteroids (i.e. methylprednisolone 2 -4 mg/kg IV) may also be considered for acute management.
- IV fluids, supplemental oxygen and bronchodilators should be considered as appropriate.
- **Grade 3 infusion reaction with MGA271:** If symptoms have resolved to baseline within 12 hours, a re-challenge may be considered at the next scheduled dose, with a 50% reduction of infusion rate. In addition, patients should be pre-medicated for this re-challenge and for any subsequent doses of MGA271 with the following: diphenhydramine hydrochloride 25-50 mg IV, oral acetaminophen 625 mg and hydrocortisone 25-100 mg IV. Patients who have a Grade 3 infusion reaction that does not resolve within 12 hours despite medical management should not receive further MGA271, pembrolizumab, or MGA012 treatment.
- **Grade 3 infusion reaction with pembrolizumab or MGA012:** If the grade 3 infusion reaction occurs with pembrolizumab or with MGA012, both MGA271 and pembrolizumab or MGA271 and MGA012 will be discontinued for that day's dose. If symptoms have resolved to baseline within 12 hours, a pembrolizumab or

MGA012 re-challenge at the next scheduled infusion day may be considered, with a 50% reduction of infusion rate. In addition, patients should be pre-medicated for this re-challenge and for any subsequent doses of pembrolizumab or MGA012 with the following: diphenhydramine hydrochloride 25-50 mg IV, oral acetaminophen 625 mg and hydrocortisone 25-100 mg IV. MGA271 dosing can be resumed with at the next scheduled infusion day if the pembrolizumab or MGA012 grade 3 infusion reaction resolved to grade 1 within 12 hours. Patients who have a Grade 3 infusion reaction that does not resolve within 12 hours despite medical management should not receive further MGA271, pembrolizumab, or MGA012 treatment.

- Patients who experience a second Grade 3 infusion reaction at the time of re-challenge of MGA271 or pembrolizumab or MGA012 (irrespective of duration of first Grade 3 reaction), will permanently discontinue MGA271, and pembrolizumab and MGA012.
- Report as an Immediately Reportable Event (IRE) within 24 hours.
- Report the event as a SAE, if appropriate.

Grade 4

- STOP THE INFUSION AND DISCONNECT THE INFUSION TUBING FROM THE PATIENT.
- TO AVOID EXACERBATION OF INFUSION REACTION OR CRS: DO NOT FLUSH THE TUBING.
- Administer diphenhydramine hydrochloride 50 mg IV, methylprednisolone 2-4 mg/kg IV (or more as considered appropriate), and other medications/treatment as medically indicated (e.g., an IL-6 receptor inhibitor or IL-6 inhibitor, an IL-2 receptor inhibitor, and/or an anti-TNF α antibody).
- Give epinephrine or bronchodilators as indicated.
- Support ventilation and blood pressure as indicated.
- Report as an IRE within 24 hours.
- Report the event as an SAE.
- Patients who have a Grade 4 infusion reaction will not receive further MGA271 or pembrolizumab or MGA012.

Grade 5

- Report as an IRE within 24 hours.
- Report the event as an SAE.

All changes in the infusion of either MGA271 or pembrolizumab or MGA012, including interruption of the infusion and its duration as well as reductions in infusion rate and duration must be recorded.

6.5.2 Immune-Related Adverse Events

Immune checkpoint blockade has been associated with several syndromes resulting from the breaking of immunological tolerance in normal tissues (28;47;62). These syndromes include but are not limited to: pneumonitis, colitis, autoimmune hepatitis, arthritis, glomerulonephritis, dermatological toxicities including toxic epidermal necrolysis (TEN) and Stevens-Johnson Syndrome (SJS), myocarditis and cardiomyopathy, hypophysitis, thyroiditis, or other autoimmune endocrinopathies. The occurrence of any of these syndromes dictates interruption, and potentially discontinuation of study drug administration pending further evaluation and reporting them to the Sponsor as adverse events of special interest (AESIs). Most low grade irAEs can be managed symptomatically. Persistent low grade or moderate toxicities may require treatment with corticosteroids or in refractory cases other immune suppressing agents such as mycophenolate or infliximab. High grade immune-related toxicities will, in almost all cases require treatment with corticosteroids.

For the purposes of the safety management, no distinction should be made as to which drug is the causative agent and both agents stopped (temporarily held or discontinued). Signs or symptoms of inflammation should be considered drug related and immune mediated, unless an alternate etiology is identified.

Temporary interruptions of MGA271, pembrolizumab, or MGA012 may be required in the event of treatment-related toxicity. General guidelines for specific toxicity regarding dosing and treatment are provided below. All toxicities will be graded according to NCI CTCAE v4.03.

6.5.2.1 Diarrhea or Colitis

Diarrhea that develops in patients while receiving pembrolizumab may reflect immune reactivity against normal colonic epithelium and careful monitoring for potential immune-related colitis should be instituted; see [Section 2.3.2.1](#) for summary of pembrolizumab safety profile.

Patients should be monitored closely for evidence of diarrhea or other change in bowel habits as well as other signs and symptoms suggestive of colitis. Patients who develop signs or symptoms including abdominal pain, bloating, nausea, vomiting, diarrhea or blood in the stools should be evaluated carefully for potential colitis.

Grade 1 diarrhea

- Closely monitor the diarrhea until resolution.

Grade 2 diarrhea

- Increase frequency of monitoring until resolution

- Consider holding the next dose of pembrolizumab or MGA012, and/or MGA271.
- Symptomatic management
- Loperamide/diphenoxylate
- Consider budesonide 9 mg once per day or divided three times per day.
- Consider management as per Grade 3 diarrhea with prolonged event > 5 to 7 days or relapsed diarrhea.

Grade 3 diarrhea

- Hospitalize patient promptly for further evaluation and management including:
- Hold pembrolizumab or MGA012, and/or MGA271
- Bowel rest
- Supplemental IV fluids with close monitoring of fluid and electrolyte status.
- Monitoring of frequency of bowel movements
- Consider imaging to rule out bowel obstruction or perforation
- Consideration of colonoscopy as appropriate
- Implementation of initial empiric immune suppression consisting of IV corticosteroids using methylprednisolone at a dosage of 2 mg/kg/day divided twice daily. As tolerated, patients may be converted to oral corticosteroids (i.e., prednisone 2 mg/kg/day divided twice daily) and tapered as appropriate guided by the patients' clinical status. Taper corticosteroids as clinically indicated.
- For patients with severe colitis, or those who do not respond to corticosteroids, additional immune suppression with anti-TNF- α antibodies (i.e., infliximab) should be considered early in the course.
- Consider restarting pembrolizumab or MGA012, and MGA271, if:
 - It is determined there is no colitis and an alternative cause of diarrhea is found
 - Diarrhea resolves to \leq CTCAE Grade 1 within 14 days

Grade 4 diarrhea

- Discontinue pembrolizumab or MGA012, and MGA271
- Treat as for Grade 3

6.5.2.2 Hepatic Toxicity

6.5.2.2.1 Elevations in Transaminases

Section 2.3.2.1 provides a summary of the pembrolizumab safety profile. Management guidelines for patients experiencing hepatic toxicity are as follows:

Grade 1 elevations

- No specific therapy required

Grade 2 elevations

- For elevations in transaminases 3 to $5 \times$ ULN (Grade 2), rule out viral and other etiologies, consider immediate oral steroids such as prednisone 60 mg /day divided twice daily, and hold MGA271 and pembrolizumab or MGA012.
- If improvement to \leq Grade 1 does not occur within 48 hours with oral steroids, consider IV steroids such as methylprednisolone at 2 mg/kg/day divided twice daily or oral steroids such as prednisone 60 to 120 mg per day, divided twice daily
- Resume pembrolizumab or MGA012, and/or MGA271, at next scheduled dose if:
- No more than one dose of pembrolizumab or MGA012 was missed and no more than 2 doses of MGA271 were missed
- If improvement to \leq Grade 1 does not occur within 14 days discontinue pembrolizumab or MGA012, and MGA271

Grade 3 elevations

- Permanently discontinue MGA271 and pembrolizumab or MGA012, for AST or ALT greater than 5 times ULN unless patient has liver metastasis and began treatment with Grade 2 AST or ALT
- For patients with liver metastasis who begin treatment with Grade 2 AST or ALT, permanently discontinue if AST or ALT increases by greater than or equal to 50% relative to baseline and lasts for at least 1 week
- Initiate IV steroids; suggest methylprednisolone at a dosage of 2 mg/kg/day divided twice daily.
- If no response to corticosteroid therapy within 3 to 5 days is observed, consider adding immune suppression therapy with mycophenolate. Infliximab is not recommended because of a potential for autoimmune hepatitis (30).
- Monitor liver function testing at least twice weekly (or more frequently as clinically appropriate in the judgment of the investigator) until transaminases have returned to Grade 1 or baseline.

Grade 4 elevations

- Discontinue pembrolizumab or MGA012, and MGA271
- Treat as for Grade 3 elevation

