 - a. Platelet count $\geq 100 \times 10^3/\mu\text{L}$ without transfusion within 28 days prior to the initiation of study drug.
 - b. Absolute neutrophil count $\geq 1.5 \times 10^3/\mu\text{L}$ in the absence of any growth factor support within 28 days prior to the initiation of study drug.
 - c. ALT/AST $\leq 3.0 \times \text{ULN}$; for patients with hepatic metastases, ALT and AST $\leq 5 \times \text{ULN}$.

- d. Total bilirubin $\leq 1.5 \times$ ULN, except patients with Gilbert's syndrome, who may enroll if the conjugated bilirubin is within normal limits.
- e. Creatinine < 2 mg/dL, or a calculated or measured creatinine clearance > 50 mL/min.

Reproductive Features:

- 11. Female patients of childbearing potential (not surgically sterilized and between menarche and 1 year postmenopause) must have a negative urine pregnancy test performed within 72 hours prior to the initiation of study drug administration. Further, female patients of childbearing potential must agree to either remain abstinent or use acceptable contraceptive measures from the time of consent through 120 days after discontinuation of study drug administration. For female patients, two forms of contraception must be utilized and may include oral, transdermal, injectable or implantable contraceptives, intrauterine device (IUD), female condom, diaphragm with spermicide, cervical cap, use of a condom by the sexual partner or a sterile sexual partner. Periodic abstinence (e.g., calendar, ovulation, symptothermal and postovulation methods) and withdrawal are not considered acceptable forms of contraception in this study.
- 12. Male patients with partners of childbearing potential must use barrier contraception. In addition, male patients should also have their partners use another method of contraception from the time of consent through 120 days after discontinuation of study drug administration.
- 13. Female patients must not be breast-feeding.

Tumor Biopsy

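### Patients with hepatic metastases may enter with Grade 2 AST/ALT, but the Grade 2 transaminase rule holds and then stops both drugs at that level without reference to baseline, contrary to the Grade 3 rule and the DLT definition.

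*Protocol*

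**What the plan says.** **Eligibility.** Protocol Section 5.1, criterion 10c, limits ALT/AST to 3.0 x ULN in general but sets a separate limit of 5 x ULN "for patients with hepatic metastases, ALT and AST". The synopsis repeats this.

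**Grade 2 management.** Section 6.5.2.2.1 applies its Grade 2 block to transaminases of 3 to 5 x ULN. After asking the site to exclude viral and other causes, it says to "consider immediate oral steroids such as prednisone 60 mg /day divided twice daily, and hold MGA271 and pembrolizumab or MGA012". If improvement to Grade 1 or better "does not occur within 14 days discontinue pembrolizumab or MGA012, and MGA271". Neither liver metastasis nor baseline grade is mentioned. The line on resuming treatment refers only to the number of doses missed.

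**Grade 3 management.** The next block stops both drugs above 5 x ULN "unless patient has liver metastasis and began treatment with Grade 2 AST or ALT". For those patients the instruction is to "permanently discontinue if AST or ALT increases by greater than or equal to 50% relative to baseline and lasts for at least 1 week". Its monitoring line accepts a return to Grade 1 or to baseline.

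**DLT definition.** Section 4.2.3 and the synopsis use the same baseline-relative test: a rise of at least 50% lasting at least 1 week.

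**Dose delays.** Section 4.5.1 allows restart once a toxicity has resolved to Grade 1 or better, including when it is judged unrelated to study drug. It discontinues both drugs when a drug-related delay exceeds 14 days. It gives no baseline alternative.

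**The concern.** A patient with liver metastases and a stable AST of 4 x ULN is eligible. The Grade 3 block and the DLT definition recognise such patients and measure change from their own starting point. The Grade 2 block does not, so on its wording an unchanged value is a reason to hold both drugs and, two weeks later, to stop them.

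Two sites could read this differently. One could hold and withdraw the patient; another could regard the value as baseline disease and continue dosing. Tolerability is a primary objective, and in Cohort 4 dosing decisions rest on groups of 3, 6 or 9 patients. A rule that can be read both ways could therefore change who is interrupted, withdrawn or replaced during the DLT period for reasons unrelated to the drugs.

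**Working it through.** The plan gives no figure to reproduce. The check sets the rules side by side, with one line of arithmetic.

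**1. Overlap of ranges.** The range opened only to patients with hepatic metastases is above 3 and up to 5 x ULN (criterion 10c). The Grade 2 block covers 3 to 5 x ULN. The first range lies wholly inside the second, so every patient who uses the wider entry limit starts at a value that the Grade 2 block addresses.

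**2. The baseline-relative threshold.** The Grade 3 block and Section 4.2.3 use 1.5 x baseline, sustained for at least 1 week.

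| Baseline (x ULN) | 1.5 x baseline (x ULN) |
|---|---|
| 3 | 4.5 |
| 4 | 6.0 |
| 5 | 7.5 |

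The threshold lies above 5 x ULN whenever baseline exceeds 5 / 1.5 = 3.33 x ULN.

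**3. The two blocks applied to a baseline of 4 x ULN.**

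- Rise to 5.5 x ULN: (5.5 - 4) / 4 = 37.5%, below 50%. The patient is exempt from the stop at 5 x ULN and does not meet the baseline-relative stop.
- Unchanged at 4 x ULN: within 3 to 5 x ULN, so the hold applies. If the value is still 4 x ULN at 14 days, Grade 1 has not been reached and both drugs are discontinued.

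On the question of stopping study drug, the lower value gets the stricter action.

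**4. Other provisions.** The resume line in the Grade 2 block counts only missed doses, but the 14-day line still applies to a patient who stays at a Grade 2 baseline. Where a hold falls under Section 4.5.1, attributing the value to metastases does not help, because restart still presumes Grade 1 or better.

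**5. Timing in Cohort 4.** Table 9 of the Protocol schedules chemistry on Days 1 and 22 of Cycle 1. A hold on Day 22 reaches its 14-day limit on Day 22 + 14 = Day 36. The DLT period ends at the third planned dose, which is Day 1 of Cycle 2 after a 6-week first cycle (Day 43). A stop under the Grade 2 block can therefore fall inside the DLT period. Sections 5.3.1 and 9.2.1 then allow replacement if the withdrawal is unrelated to drug toxicity.

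**The case against.** The strongest reply concerns scope. Section 6.5.2.2 addresses patients with hepatic toxicity, within a section on immune-related events. Section 6.5.2 calls its content general guidelines and presumes drug causation only when no other cause is found. The Grade 2 block itself begins by excluding other causes, and known liver metastases are an obvious one. The Grade 3 provision for patients who start at Grade 2 would also have little use if the same patients had already been stopped. A sensible investigator might well continue treatment.

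That reading is plausible, but it is not written down. The hold is not made conditional on the cause, and Section 4.5.1 asks for Grade 1 even when the toxicity is unrelated. The explicit exception one block later makes its absence from the Grade 2 block harder to read as implied.

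Several stronger inferences are tempting, and here the reply stands:

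- *Patients would be given steroids for their disease.* The Grade 2 block only asks that steroids be considered.
- *They would appear as drug-related adverse events.* Section 7.8.1 allows a laboratory abnormality that interrupts treatment to be reported as an AE. However, Section 7.8.2.4 counts a pre-existing event as treatment-emergent only if it worsens, Section 7.8.5 leaves causality to the investigator, and Section 7.8.6 refers to change from baseline. Entry into the drug-related tables is not shown.
- *The rule applies before the first dose.* On Day 1 no drug has been given, so no drug toxicity is possible.
- *The pembrolizumab results can still be protected.* Section 2.3.1.1.2 says those cohorts are closed and their combination treatment is complete.

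**Conclusion.** The contradiction is real and lies in the text: eligibility, the Grade 2 block, the Grade 3 block, the DLT definition and the restart condition do not agree for a patient who enters with Grade 2 AST/ALT. It covers the whole of the extra entry range, above 3 and up to 5 x ULN.

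Its effect on the results cannot be sized. The documents do not give the share of patients entering in that range. One patient is 1/15 = 6.7 percentage points of a full Cohort 4 and 1/3 = 33 points of its first group, but that holds for any single patient and is not an estimate of bias.

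The consequence that can be supported is conditional. If such patients enrol in Cohort 4 and sites read the block differently, interruptions, withdrawals and DLT-period replacement could differ by site. This rests on a literal reading of the Grade 2 block and on a transaminase value that stays at baseline. The correction should be made because a stated rule can stop an eligible patient at an unchanged value and the repair is cheap.

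**What to change.** The sponsor's medical team should reconcile criterion 10c (Section 5.1 and synopsis), the Grade 2 and Grade 3 blocks of Section 6.5.2.2.1, the hepatic DLT definition (Section 4.2.3 and synopsis) and the restart and 14-day conditions of Section 4.5.1. Eligibility, hold, restart and stop rules should then be consistent for patients who enter with Grade 2 AST/ALT. Which passage changes is a clinical decision, and no view is offered here on which rule is right.

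The cost is one protocol clarification, communicated to sites treating Cohort 4. No SAP change is essential: SAP Section 6.7.2 already summarises laboratory changes from baseline and allows shift tables.
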